## 10.7. Appendix 7: ECG Findings of Potential Clinical Concern

#### ECG Findings That May Qualify as AEs

- Marked sinus bradycardia (rate <40 bpm) lasting minutes.
- New PR interval prolongation >280 msec.
- New prolongation of QTcF to >480 msec (absolute) or by ≥60 msec from baseline.
- New-onset atrial flutter or fibrillation, with controlled ventricular response rate: ie, rate <120 bpm.
- New-onset type I second-degree (Wenckebach) AV block of >30 seconds' duration.
- Frequent PVCs, triplets, or short intervals (<30 seconds) of consecutive ventricular complexes.

## ECG Findings That May Qualify as SAEs

- QTcF prolongation >500 msec.
- New ST-T changes suggestive of myocardial ischemia.
- New-onset left bundle branch block (QRS > 120 msec).
- New-onset right bundle branch block (QRS >120 msec).
- Symptomatic bradycardia.
- Asystole:
  - In awake, symptom-free participants in sinus rhythm, with documented periods of asystole ≥3.0 seconds or any escape rate <40 bpm, or with an escape rhythm that is below the AV node.
  - In awake, symptom-free participants with atrial fibrillation and bradycardia with 1 or more pauses of at least 5 seconds or longer.
  - Atrial flutter or fibrillation, with rapid ventricular response rate: rapid = rate >120 bpm.
- Sustained supraventricular tachycardia (rate >120 bpm) ("sustained" = short duration with relevant symptoms or lasting >1 minute).

- Ventricular rhythms >30 seconds' duration, including idioventricular rhythm (heart rate <40 bpm), accelerated idioventricular rhythm (HR >40 bpm to <100 bpm), and monomorphic/polymorphic ventricular tachycardia (HR >100 bpm (such as torsades de pointes)).
- Type II second-degree (Mobitz II) AV block.
- Complete (third-degree) heart block.

## ECG Findings That Qualify as SAEs

- Change in pattern suggestive of new myocardial infarction.
- Sustained ventricular tachyarrhythmias (>30 seconds' duration).
- Second- or third-degree AV block requiring pacemaker placement.
- Asystolic pauses requiring pacemaker placement.
- Atrial flutter or fibrillation with rapid ventricular response requiring cardioversion.
- Ventricular fibrillation/flutter.
- At the discretion of the investigator, any arrhythmia classified as an adverse experience.

The enumerated list of major events of potential clinical concern are recommended as "alerts" or notifications from the core ECG laboratory to the investigator and Pfizer study team, and not to be considered as all inclusive of what to be reported as AEs/SAEs.

## 10.8. Appendix 8: Alternative Measures During Public Emergencies

The alternative study measures described in this section are to be followed during public emergencies, including the COVID-19 pandemic. This appendix applies for the duration of the COVID-19 pandemic globally and will become effective for other public emergencies only upon written notification from Pfizer.

Use of these alternative study measures are expected to cease upon the return of business as usual circumstances (including the lifting of any quarantines and travel bans/advisories).

## 10.8.1. Study Intervention

If the safety of a trial participant is at risk because they cannot complete required evaluations or adhere to critical mitigation steps, then discontinuing that participant from study intervention must be considered.

#### 10.8.2. Adverse Events and Serious Adverse Events

If a participant has COVID-19 during the study, this should be reported as an AE or SAE and appropriate medical intervention provided.

It is recommended that the investigator discuss temporary or permanent discontinuation of study intervention with the study medical monitor.

## 10.10. Appendix 9: Abbreviations

The following is a list of abbreviations that may be used in the protocol.

Abbreviation	Term	
Abs	absolute	
ADL	activities of daily living	
AE	adverse event	
ALT	alanine aminotransferase	
AST	aspartate aminotransferase	
AUC	area under the curve	
AUC last	area under the plasma concentration-time curve from time zero to	
	the time of the last quantifiable concentration	
AUCinf	area under the plasma concentration-time curve from time zero	
	extrapolated to infinite time	
AV	atrioventricular	
BE	bioequivalence	
β-hCG	beta-human chorionic gonadotropin	
BMI	body mass index	
BP	blood pressure	
bpm	beats per minute	
BUN	blood urea nitrogen	
CFR	Code of Federal Regulations	
CI	confidence interval	
CIOMS	Council for International Organizations of Medical Sciences	
CK	creatine kinase	
$C_{max}$	maximum plasma concentration	
$CO_2$	carbon dioxide (bicarbonate)	
COVID-19	coronavirus disease 2019	
CRF	case report form	
CRO	contract research organization	
CRU	clinical research unit	
CSR	clinical study report	
CT	clinical trial	
DC	discontinuation	
DCT	data collection tool	
DILI	drug-induced liver injury	
DMC	data monitoring committee	
DNA	deoxyribonucleic acid	
EC	ethics committee	
ECC	Emergency Contact Card	
ECG	electrocardiogram	
eCRF	electronic case report form	
EDB	exposure during birth	

Abbreviation	Term
EDP	exposure during pregnancy
EMA	European Medicines Agency
EU	European Union
EudraCT	European Clinical Trials Database
$f_2$	similarity factor
FDA	Food and Drug Administration
FSH	follicle-stimulating hormone
GCP	Good Clinical Practice
GGT	gamma-glutamyl transferase
HBcAb	hepatitis B core antibody
HBsAb	hepatitis B surface antibody
HBsAg	hepatitis B surface antigen
HC1	hydrochloride
HCVAb	hepatitis C antibody
HIV	human immunodeficiency virus
HRT	hormone replacement therapy
IB	investigator's brochure
ICD	informed consent document
ICH	International Council for Harmonisation
IND	investigational new drug application
INR	international normalized ratio
IP	investigational product
IRB	institutional review board
IV	intravenous
LBBB	left bundle branch block
LFT	liver function test
MCH	mean corpuscular hemoglobin
MCHC	mean corpuscular hemoglobin concentration
MCV	mean corpuscular volume
msec	millisecond
N	number of participants
PCR	polymerase chain reaction
PD	pharmacodynamic(s)
PK	pharmacokinetic(s)
PT	prothrombin time
PVC	premature ventricular complex
QTc	corrected QT
QTcF	corrected QT (Fridericia method)
qual	qualitative
RBC	red blood cell
RNA	ribonucleic acid
SAE	serious adverse event

Abbreviation	Term
SAP	statistical analysis plan
SARS-CoV-2	severe acute respiratory syndrome coronavirus 2
SoA	schedule of activities
SOP	standard operating procedure
SRSD	single reference safety document
SToD	study team on demand
SUSAR	suspected unexpected serious adverse reaction
t 1/2	terminal elimination half-life
TBili	total bilirubin
THC	tetrahydrocannabinol
$T_{max}$	time to first occurrence of C max
ULN	upper limit of normal
US	United States
USPI	United States Package Insert
WBC	white blood cell
WOCBP	woman of childbearing potential

1. AMENDMENTS FROM PREVIOUS VERSION(S)

None.

2. INTRODUCTION

2.1. Study Design

This will be a 2 Cohort, open-label, randomized, single dose study in healthy adult male and/or female participants. Cohort 1 will be crossover with 3 treatments, 3 periods, 6 sequences. Cohort 2 will be crossover with 2 treatments, 2 periods, 2 sequences. Approximately 36 participants will be enrolled in each of Cohort 1 and Cohort 2. Participants enrolled in Cohort 1 will not be eligible for Cohort 2 and vice versa. Dropouts for non-safety reasons may be replaced at the discretion of the sponsor and investigator. Participants in Cohort 1 will be assigned to 1 of the 6 sequences according to a computer-generated randomization schedule (see Table 1). Participants in Cohort 2 will be assigned to 1 of the 2 sequences according to a computer-generated randomization schedule (see Table 2).

Sequence	Period 1	Washout Period	Period 2	Washout Period	Period 3
1 (N = 6)	A		В		С
2(N=6)	В	At least 7 days	С	At least 7 days	A
3 (N = 6)	С		A		В
4 (N = 6)	A		С		В
5 (N = 6)	В		A		С
6 (N = 6)	С		В		A

Table 1.	Study	Schematic:	Sequences	for Cohort 1
	•/			

Treatment A: Prazosin HCL 1 x 2 mg capsule manufactured at the current site (Barceloneta) under fasting conditions (Reference).

Treatment B: Prazosin HCl 1 x 2 mg capsule manufactured at the proposed site (Ascoli) under fasting conditions (Test 1).

Treatment C: Prazosin HCl 2×1 mg capsule manufactured at the proposed site (Ascoli) under fasting conditions (Test 2).

Table 2. Study Schematic: Sequences for Cohort 2

Sequence	Period 1	Washout Period	Period 2
1 (N = 18)	D	At least 7 days	Ε
2 (N = 18)	Ε	At least / days	D

Treatment D: Prazosin HCl 1 x 5 mg capsule manufactured at the current site (Barceloneta) under fasting conditions (Reference).

Treatment E: Prazosin HCl 1 x 5 mg capsule manufactured at the proposed site (Ascoli) under fasting conditions (Test).

On Day 1 of each period, participants will receive a single dose of investigational product as per randomization schedule. Study treatments will be administered with approximately 240 mL of ambient temperature water under fasting conditions (overnight fast and no food until 4 hours after dosing). Water will be allowed without restriction until 1 hour prior to dosing and may be consumed without restriction beginning 1 hour after dosing.

Blood samples for the analysis of prazosin in plasma will be obtained predose (immediately prior to dosing) and postdose as outlined in Schedule of Activities (Study Protocol' SoA) table. Tolerability and safety will be assessed for all treatments by monitoring AEs.

2.2. Study Objectives

Primary:

- To demonstrate bioequivalence between prazosin HCL 1 and 2 mg capsules manufactured at the proposed site (Ascoli) versus prazosin HCl 2 mg capsules manufactured at the current site (Barceloneta) under fasting conditions in healthy adult participants.
- To demonstrate bioequivalence between prazosin HCl 5 mg capsules manufactured at the proposed site (Ascoli) versus prazosin HCl 5 mg capsules manufactured at the current site (Barceloneta) under fasting conditions in healthy adult participants.

Secondary:

• To evaluate the safety and tolerability of prazosin HCl capsules.

	Page 6 of 17	
	PFIZER CONFIDENTIAL	

3. INTERIM ANALYSES, FINAL ANALYSES AND UNBLINDING

No formal interim analysis will be conducted for this study. As this is an open-label study, the sponsor may conduct unblinded reviews of the data during the course of the study for the purpose of safety assessment, facilitating PK/PD modeling, and/or supporting clinical development.

As this will be an open-label study, there is no formal unblinding of the randomization code.

4. HYPOTHESES AND DECISION RULES

4.1. Statistical Hypotheses

4.1.1. Bioequivalence Hypotheses

The alternative hypothesis of bioequivalence ($H_1: \theta_L \leq = \mu_T - \mu_R \leq = \theta_U$), and the null hypothesis of inequivalence ($H_0: \mu_T - \mu_R \leq \theta_L$ or $\mu_T - \mu_R \geq \theta_U$) can be expressed as the following two separate one-sided hypotheses:

HoA: $\mu_T - \mu_R < \theta_L$

*H*₁*A*: $\mu_T - \mu_R >= \theta_L$

Hob: $\mu_T - \mu_R > \theta_U$

*H*_{1B}: $\mu_T - \mu_R <= \theta_U$

where μ_T and μ_R represent the average bioavailability on a log scale for the Test and *Reference products, respectively and* $[\theta_L, \theta_U]$ *defines the bioequivalence range.*

Bioequivalence of the Test treatment to Reference treatment will be concluded if the 90% confidence intervals for the ratios of adjusted geometric means for prazosin AUC_{last} and C_{max} fall entirely within the acceptance region of (80%, 125%).

4.2. Statistical Decision Rules

Bioequivalence will be demonstrated if both AUC_{last} and C_{max} meet the conditions of bioequivalence using their respective method outlined in Section 4.2.1.

4.2.1. Average Bioequivalence Decision Rules

The two one-sided hypotheses are tested at the α = 0.05 levels of significance for log-transformed AUC_{last} and C_{max} by constructing the 90% confidence interval for the ratio between the test and reference geometric means.

Bioequivalence will be demonstrated if the estimated 90% confidence interval for the ratios (Test/Reference) of adjusted geometric means for AUC_{last} and C_{max} fall entirely within (80%, 125%).

5. ANALYSIS SETS

5.1. Enrolled/Randomly Assigned to Study Intervention

Participants will be randomized into the study provided they have satisfied all participant eligibility criteria.

5.2. Pharmacokinetic (PK) Analysis Set

5.2.1. Concentration Analysis Set

All participants randomized and treated who have at least 1 concentration in at least 1 treatment period.

5.2.2. Parameter Analysis Set

The PK parameter analysis population is defined as all participants randomized and treated who have at least 1 of the PK parameters of primary interest in at least 1 treatment period.

5.3. Pharmacodynamic Analysis Set

None.

5.4. Safety Analysis Set

All participants randomly assigned to study intervention and who take at least 1 dose of investigational product.

5.5. Other Analysis Sets

None.

5.6. Treatment Misallocations

All analyses will be performed on an "as-treated" basis and will not include data from participants who are randomized but not treated.

If a participant takes a treatment that is not consistent with the treatment they are randomized to, for example takes a treatment out of sequence or takes the same treatment twice, then they will be reported under the treatment that they actually received for all safety, PK and pharmacodynamic analyses, where applicable.

 Page 8 of 17	
PFIZER CONFIDENTIAL	

5.7. Protocol Deviations

Participants who experience events that may affect their PK profile (eg, lack of compliance with dosing) may be excluded from the PK analysis. At the discretion of the pharmacokineticist a concentration value may also be excluded if the deviation in sampling time is of sufficient concern or if the concentration is anomalous for any other reason.

A full list of protocol deviations will be compiled and reviewed to identify major and minor deviations prior to database closure.

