#### 8.4. Pharmacokinetics

Blood samples of approximately 4 mL, to provide approximately 1.5 mL plasma, will be collected for measurement of plasma concentrations of prazosin as specified in the SoA. Instructions for the collection and handling of biological samples will be provided in the laboratory manual or by the sponsor. The actual date and time (24-hour clock time) of each sample will be recorded.

The actual times may change, but the number of samples will remain the same. All efforts will be made to obtain the samples at the exact nominal time relative to dosing. Collection of samples up to and including 10 hours after dose administration that are obtained within 10% of the nominal time (eg, within 6 minutes of a 60-minute sample) relative to dosing will not be captured as a protocol deviation, as long as the exact time of the collection is noted on the source document and data collection tool (eg, CRF/DCT). Collection of samples more than 10 hours after dose administration that are obtained ≤1 hour away from the nominal time relative to dosing will not be captured as a protocol deviation, as long as the exact time of the collection is noted on the source document and data collection tool (eg, CRF/DCT).

Genetic analyses will not be performed on these plasma samples. Participant confidentiality will be maintained.

Samples collected for measurement of plasma concentrations of prazosin will be analyzed using a validated analytical method in compliance with applicable standard operating procedures (SOPs).

The PK samples must be processed and shipped as indicated in the instructions provided to the investigator site to maintain sample integrity. Any deviations from the PK sample handling procedure (eg, sample collection and processing steps, interim storage or shipping conditions), including any actions taken, must be documented and reported to the sponsor. On a case-by-case basis, the sponsor may make a determination as to whether sample integrity has been compromised.

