#### 9. STATISTICAL CONSIDERATIONS

Detailed methodology for summary and statistical analyses of the data collected in this study is outlined here and further detailed in a SAP, which will be maintained by the sponsor. The SAP may modify what is outlined in the protocol where appropriate; however, any major modifications of the primary endpoint definitions or their analyses will also be reflected in a protocol amendment.

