#### 9.3. Statistical Analyses

The SAP will be developed and finalized before any analyses are performed and will describe the analyses and procedures for accounting for missing, unused, and spurious data. This section is a summary of the planned statistical analyses of the primary and secondary endpoints.

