5.7.2. Deviations Assessed Post-Randomization

A full list of protocol deviations for the study report will be compiled prior to database closure. Any significant deviation from the protocol will be reviewed prior to database closure and a decision taken regarding evaluation for each analysis population.

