7.3. Pharmacokinetic Parameters

Actual PK sampling times will be used in the derivation of PK parameters.

If a PK parameter cannot be derived from a participant's concentration data, the parameter will be coded as NC (ie, not calculated). Note that NC values will not be generated beyond the day that a participant discontinues.

In summary tables, statistics will be calculated by setting NC values to missing; and statistics will be presented for a particular treatment with \geq 3 evaluable measurements. For statistical analyses (ie, analysis of variance), PK parameters coded as NC will also be set to missing; and analyses will not be performed for a particular parameter if more than 50% of the data are NC.

If an individual participant has a known biased estimate of a PK parameter (for example due to an unexpected event that might occur before all the compound is adequately absorbed in the body), this will be footnoted in summary tables and will not be included in the calculation of summary statistics or statistical analyses.

If an individual participant has a predose concentration ≤ 5 percent of the C_{max} value, then that participant's data can be included in all pharmacokinetic measurements and calculations without any adjustments. If the predose value is >5 percent of C_{max} , the PK parameters for that period will be excluded for that participant from all bioequivalence evaluations.

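### SAP 5.7 lets a single concentration be dropped as anomalous without a criterion, a documented cause or masking to treatment, and not necessarily before treatment-labelled results are seen

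*SAP*

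**What the plan says.** SAP 5.7 contains two discretionary rules.

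- **Single concentrations.** At the pharmacokineticist's judgement a value may be "excluded if the deviation in sampling time is of sufficient concern or if the concentration is anomalous for any other reason".
- **Participants.** "Participants who experience events that may affect their PK profile (eg, lack of compliance with dosing) may be excluded from the PK analysis". Dosing non-compliance is the only example, and the list is not closed.

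Other provisions bear on these rules:

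- SAP 5.7 requires a list of protocol deviations, reviewed before the database closes. SAP 5.7.2 adds: "Any significant deviation from the protocol will be reviewed prior to database closure and a decision taken regarding evaluation for each analysis population".
- SAP 7.3 deals with a PK parameter estimate known to be biased: "this will be footnoted in summary tables and will not be included in the calculation of summary statistics or statistical analyses". It also excludes a period's parameters when the predose concentration is above 5% of Cmax.
- Protocol 8.4 sets sampling-time windows and requires sample-handling deviations to be documented. It adds: "On a case-by-case basis, the sponsor may make a determination as to whether sample integrity has been compromised".
- SAP 8.2 lists all concentrations with actual times and asks for justification in the report of any alternative to the planned analysis.
- SAP 3 says that, the study being open-label, the "sponsor may conduct unblinded reviews of the data during the course of the study for the purpose of safety assessment, facilitating PK/PD modeling" and to support clinical development.
- Protocol 9.3 promises that the SAP "will describe the analyses and procedures for accounting for missing, unused, and spurious data".

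**The concern.** For a concentration judged anomalous, the SAP gives discretion where the protocol promised a procedure. The study is open-label, so whoever judges the value may know which product it came from. Protocol Table 5 takes Cmax directly from the observed data, so removing one peak sample replaces that participant's Cmax for the period with the next-highest value. A reference peak removed pushes the Test/Reference ratio up; a test peak removed pushes it down.

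A choice made with treatment known can lean, even without intent, towards the exclusion that helps the result. The error rate at the equivalence limit is then no longer the 5% on which the 90% interval rests. A full listing lets an assessor put the value back and re-run the model. It does not show whether the value was removed for a cause or for its effect.

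**Working it through.** **1. The plan's own figures.** Inputs from Protocol 9.5: true ratio 0.95, within-participant SD 0.198 on the log scale, 30 evaluable in Cohort 1 and 32 in Cohort 2. SAP 4.2.1 gives limits of 80-125% and two one-sided tests at 0.05. The standard error of the log ratio is 0.198 × √(2/n), which is 0.0511 for n = 30 and 0.0495 for n = 32. Power, integrated over the residual-variance distribution:

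- Cohort 1 (df = 2n − 4 = 56): 0.953, and the product for two parameters is 0.908.
- Cohort 2 (df = n − 2 = 30): 0.960, and the product is 0.921.

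The stated 95% per parameter and roughly 90% overall reproduce. The point disputes no figure in the plan.

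**2. What each safeguard reaches.**

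| Provision | Covers | A single value called anomalous? |
|---|---|---|
| SAP 5.7, 5.7.2 review before closure | Protocol deviations | Only if it is also a deviation |
| SAP 7.3 footnote and predose rule | PK parameters | No |
| Protocol 8.4 windows, handling records | Timing and handling deviations | Only if that is the cause |
| SAP 8.2 justification | Model outliers, transformations | No |
| SAP 8.2 listing | All concentrations | Shows the value, not the reason for removal |

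No provision places database closure, or the exclusion decision, before treatment-labelled PK is seen.

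**3. Hand check on one peak (Cohort 2).** Assume the dropped reference peak is 10% above the next sample. The mean log ratio moves by ln(1.10)/32 = 0.0953/32 = 0.0030, or 0.0030/0.0495 = 0.06 standard errors. At the limit, an upper-tail probability of 5% at 1.645 becomes 5.65% at 1.585. The expected effect is therefore small, and larger if the most helpful peak can be chosen.

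**4. Simulation, one peak.** 20,000 trials per setting, true ratio 0.80, the 15 postdose times in the Schedule of Activities, a one-compartment model with half-life 2-3 h (Protocol 2.2.1), and SD of ln Cmax set to 0.198. Assumptions not in the documents are an absorption rate of about 1/h and sample noise of 2-15%. The most favourable peak is dropped only when Cmax would otherwise fail.

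| Sample noise | 2% | 5% | 10% | 15% |
|---|---|---|---|---|
| Cohort 2, planned | 5.0% | 4.8% | 5.0% | 4.8% |
| Cohort 2, one selective peak | 5.5% | 5.9% | 6.8% | 7.9% |
| Cohort 1 (B vs A), planned | 4.9% | 5.0% | 4.8% | 4.9% |
| Cohort 1, one selective peak | 5.6% | 5.9% | 6.7% | 7.7% |

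Dropping peaks by a rule blind to treatment gives 4.8-5.0%.

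**5. Simulation, participants.** In Cohort 2 (100,000 trials, true ratio 0.80), 1, 2 or 3 participants have an event that does not in truth affect PK, and the trial passes if any keep-or-drop choice passes. Error per parameter is 5.8%, 6.6% and 7.5%, against 5.0% planned. Excluding all of them by a fixed rule gives 4.9-5.0%. In Cohort 1 (30,000 trials) the figures are 5.9%, 6.7% and 7.7%, against 5.2% planned.

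**6. Both parameters together.** Bioequivalence needs AUClast and Cmax. In Cohort 2 with three discretionary participants and both true ratios at 0.80 (assumed correlation 0.5-0.8), the error goes from 1.2-2.6% to 2.0-4.1%, still below 5%. With the other ratio at 0.95 it goes from 4.9-5.2% to 7.5-7.8%.

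**The case against.** The best defence is that the plan is less open than SAP 5.7 looks alone. Deviations are listed and reviewed before closure, and significant ones are decided on for each population. Dosing non-compliance, the SAP's own example, falls under that review. Major changes to the primary analysis need an amendment (Protocol 9: "any major modifications of the primary endpoint definitions or their analyses will also be reflected in a protocol amendment"). All concentrations are listed, so any exclusion can be undone. Unblinded reviews are permitted but none is scheduled, and that the pharmacokineticist would see their output is an inference. The simulated conduct is not described anywhere in the SAP, and the masked or fixed-rule comparison is nominal almost by construction. The effect of one choice is small: 5.8 − 5.0 = 0.8 points for one participant, 5.5 − 5.0 = 0.5 points for one peak at 2% noise.

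Most of this stands and limits the point. It does not cover a value that is no deviation at all but is judged anomalous with treatment known.

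Some stronger readings are tempting, but the documents do not support them:

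- *That no timing or documentation rule exists for any exclusion.* For participants with significant deviations, SAP 5.7 and 5.7.2 supply a compiled list and a decision before closure.
- *That SAP 5.7 and 7.3 contradict each other.* The first concerns events that may affect PK, and makes exclusion optional. The second concerns a parameter estimate known to be biased, and makes exclusion mandatory. The triggers differ.
- *That the outlier step in SAP 8.2 can replace the primary analysis.* SAP 4.2, 4.2.1 and 8.2 fix the decision rule, and the outlier step reads as a sensitivity analysis.
- *That the error could reach 11-30%.* This requires freely dropping the one to three lowest-ratio participants after a failed result. SAP 5.7 limits participant exclusion to those with an event.

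**Conclusion.** The point holds for single concentrations. SAP 5.7 has an open-ended ground for exclusion, with no criterion, recorded cause or masking, in an open-label study where one sample can set a primary endpoint. For participants it holds in part: exclusion is optional and unmasked, but decisions on significant deviations must come before database closure.

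The error figures in the working (up to about 8% per parameter for one peak, 7.5% for three participants in Cohort 2) assume normal data, SD 0.198, a true ratio exactly at 0.80 and choices made by looking at the result. The noise levels, absorption rate and numbers of participants are also assumed. They bound what the discretion could do; nothing in the documents suggests such conduct is intended. The source of the inflation is choice informed by the result, not exclusion itself. This merits a change to the SAP but casts no doubt on the design, sample size or decision rule.

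**What to change.** In SAP 5.7, remove the catch-all ground and state that:

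1. Concentrations, profiles or participants are excluded from the bioequivalence analysis only for a documented cause, such as a dosing error, sample mishandling, a recorded time error or the existing predose rule.
2. Each decision is made and signed off on PK listings without treatment codes, before any by-treatment PK output is produced.
3. The report lists each exclusion with its cause.

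A cross-reference from SAP 5.7 to 7.3 would help readers but is optional. SAP 7.2, which governs summary tables and median plots, and SAP 8.2 need no change.

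The cost is a few sentences, one extra set of listings, and slightly less flexibility for the pharmacokineticist. In return, a legitimate exclusion is easier to defend to an assessor.
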